5.1.3.2. Patients Not Eligible for the Substudy

Beginning at Week 52,

- Patients with an IGA ≥ 3 who
 - are in the baricitinib 2-mg, 1-mg, and placebo treatment groups will be automatically rerandomized at a 1:1 ratio to baricitinib 2-mg QD or baricitinib 4-mg QD.

- are in the baricitinib 4-mg treatment group will remain on 4-mg QD (see “Rescue during Period 3” Section 7.7.5.2).
- Patients with an IGA 0, 1, or 2 who
 - are in the baricitinib 4-mg or 2-mg treatment groups and who are not eligible for the substudy (i.e., have study drug interrupted at Week 52, or have received high- or ultra-high potency TCS in the previous 14 days), or are in the placebo or baricitinib 1-mg groups will continue in their current treatment group.
 - Patients who experience a worsening of symptoms of AD such that IGA increases to ≥ 3 will be rerandomized at a 1:1 ratio to baricitinib 2-mg QD or baricitinib 4-mg QD. Patients in the baricitinib 4-mg group will remain on 4-mg.

This option for rescue is only available once for each patient and will be assigned by IWRS; investigators will remain blinded to treatment assignments. The investigator may reinstate background TCS therapy (e.g., triamcinolone 0.1% cream and/or hydrocortisone 2.5% ointment), provided the patients are not currently using TCS, and may prescribe high- or ultra-high-potency TCS following the guidelines for use of rescue therapies (see Section 7.7.5).

Once a patient has an IGA ≥ 3 in Period 3, the investigator will know that a patient is on the highest dose of baricitinib that he/she will receive in the study; therefore, if AD symptoms remain unacceptable then discontinuation should be considered.

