**Table JAIN.6.3. Treatment Groups and Comparisons for the 104-Week Interim and Final DBL Analysis Population**

Study Period	Analysis Population	Treatment Group	Abbreviation	Analyses Category
Long-Term Extension Period (Period 3 and Period 4)	LTE Substudy Population	Bari 4-mg in Period 2, were re-randomized to (Bari 4-mg or Bari 2-mg) in Period 3/Period 4;	Bari 4-mg/4-mg Bari 4-mg/2-mg	Efficacy
	LTE Substudy Population with IGA(0,1) at Week 52	Bari 2-mg in Period 2, were re-randomized to (Bari 2-mg or Bari 1-mg) in Period 3/Period 4.	Bari 2-mg/2-mg Bari 2-mg/1-mg	Efficacy for Subsetting IGA(0,1) at Week 52
	LTE Substudy Relapse Population	Bari 4-mg in Period 2, were re-randomized to (Bari 4-mg or Bari 2-mg) in Period 3/Period 4, retreated with presubstudy of Bari 4-mg when Relapse occurred;  Bari 2-mg in Period 2, were re-randomized to (Bari 2-mg or Bari 1-mg) in Period 3/Period 4, retreated with presubstudy of Bari 2-mg when Relapse occurred.	Bari 4-mg/4-mg/4-mg Bari 4-mg/2-mg/4-mg  Bari 2-mg/2-mg/2-mg Bari 2-mg/1-mg/2-mg	Time to Relapse
	LTE Non-responder Population	Bari 4-mg stays Bari 4-mg in Period 2 & Period 3/Period 4;	Bari 4-mg Bari 2-mg /2-mg Bari 2-mg/4-mg Bari 1-mg/2-mg Bari 1-mg/4-mg PBO/Bari 2-mg PBO/Bari 4-mg	Efficacy

	(Bari 2-mg, Bari 1-mg or Placebo) were re-randomized to (Bari 2-mg or Bari 4-mg) in Period 3.		
Long-Term Extension (LTE) Responders & Partial Responders who did not enter the Substudy	Bari 4-mg, Bari 2-mg Bari 1-mg, Placebo will continue on the same treatment	Bari 4-mg Bari 2-mg Bari 1-mg Placebo	Efficacy
Safety Population	Bari 4-mg, Bari 2-mg Bari 1-mg, Placebo who continuously got treated from baseline and censored in case of dose change.	Bari 4-mg Bari 2-mg Bari 1-mg Placebo All Bari	Safety

Abbreviations: Bari = baricitinib; IGA = Investigator's Global Assessment for AD; LTE = Long-Term Extension; PBO = placebo.

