- Duration of exposure to investigational product (including exposure after the initiation of rescue therapy): *date of last dose of study drug including rescue – date of first dose of study drug + 1*

Duration of exposure (in days) for the “PBO/BARI 1-mg to BARI 2-mg” and the “PBO/BARI 1-mg/BARI 2-mg to BARI 4-mg” groups will be calculated as follows:

- Duration of exposure to investigational product (including exposure after the initiation of rescue therapy): *date of last dose of study drug including rescue – date of first dose of study drug after the switch + 1*

Last dose of study drug including rescue is calculated as last date on study drug. See the Compound level safety standards for more details.

Total patient-years (PY) of exposure will be reported for each treatment group for overall duration of exposure. Descriptive statistics will be provided for patient-days of exposure, and the frequency of patients falling into different exposure ranges in addition to cumulative exposures will be summarized.

Exposure ranges will be reported in weeks using the following:

- ≥4 weeks, ≥8 weeks, ≥12 weeks, ≥16 weeks, ≥24 weeks, ≥52 weeks, ≥76 weeks, ≥104 weeks, ≥120 weeks, ≥136 weeks, ≥152 weeks, ≥168 weeks, ≥184 weeks and ≥200 Weeks
- >0 to <4 weeks, ≥4 weeks to <8 weeks, ≥8 weeks to <12 weeks, ≥12 to <16 weeks, ≥16 to 24 weeks, ≥24 to 52 weeks, ≥52 to 76 weeks, ≥76 to 104 weeks, and ≥104 to 120 weeks, ≥120 to 136 weeks, ≥136 to 152 weeks, ≥152 to 168 weeks, ≥168 to 184 weeks, ≥184 to 200 weeks, ≥200 Weeks

The exposure ranges for the interim lock(s) will be adjusted accordingly.

**For Week-104 interim analysis**, exposure ranges will be reported in weeks using the following:

- ≥52 weeks, ≥60 weeks, ≥68 weeks, ≥76 weeks, ≥92 weeks, and ≥104 weeks
- ≥52 weeks to <60 weeks, ≥60 weeks to <68 weeks, ≥68 to <76 weeks, ≥76 to 92 weeks, ≥92 to 104 weeks, and ≥104 weeks

**For final analysis**, exposure ranges will be reported in weeks using the following:

- ≥52 weeks, ≥60 weeks, ≥68 weeks, ≥76 weeks, ≥92 weeks, ≥104 weeks, ≥120 weeks, ≥136 weeks, ≥152 weeks, ≥168 weeks, ≥184 weeks, ≥200 weeks
- ≥52 weeks to <60 weeks, ≥60 weeks to <68 weeks, ≥68 to <76 weeks, ≥76 to 92 weeks, ≥92 to 104 weeks, and ≥104 to 120 weeks, ≥120 to 136 weeks, ≥136 to 152 weeks, ≥152 to 168 weeks, ≥168 to 184 weeks, ≥184 to 200 weeks, ≥200 Weeks

Overall exposure will be summarized in total PY, which is calculated according to the following formula:

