### 6.13.1. Adverse Events

Adverse events are recorded in the eCRFs. Each AE will be coded to System Organ Class (SOC) and Preferred Term (PT) using the Medical Dictionary for Regulatory Activities

(MedDRA) version that is current at the time of DBL. Severity of AEs is recorded as mild, moderate, or severe.

A treatment-emergent adverse event (TEAE) is defined as an event that either first occurred or worsened in severity after the first dose of study treatment and on or prior to the last visit date during the analysis period. The analysis period is defined as the treatment period plus up to 30 days off-drug follow-up time.

Adverse events are classified based upon the MedDRA PT. The MedDRA Lowest Level Term (LLT) will be used in defining which events are treatment-emergent. The maximum severity for each LLT during the baseline period up to first dose of the study medication will be used as baseline. If an event with missing severity is pre-existing during the baseline period, and persists during the treatment period, then the baseline severity will be considered mild for determining treatment-emergence (that is, the event is treatment-emergent if the severity is coded moderate or severe postbaseline and not treatment-emergent if the severity is coded mild postbaseline). If an event occurring postbaseline has a missing severity rating, then the event is considered treatment-emergent unless the baseline rating is severe, in which case the event is not a treatment-emergent. The day and time for events where onset is on the day of the first dose of study treatment will both be used to distinguish between pretreatment and posttreatment to derive treatment-emergence. Should there be insufficient data for AE start date to make this comparison (for example, the AE start year is the same as the treatment start year, but the AE start month and day are missing), the AE will be considered treatment-emergent.

In general, summaries will include the number of patients in the safety population (N), frequency of patients experiencing the event (n), and relative frequency (that is, percentage;  $n/N*100$ ). For any events that are gender-specific based on the displayed PT, the denominator used to compute the percentage will only include patients from the given gender.

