For selected safety topics, incidence rate (IR) per 100 patient-years of observation (PYR) will be provided for the Week 52, Week 104, and final analyses. See the Compound level safety standards for more details.

Adverse Events and Treatment Emergent AEs will be replicated based on the Safety Censoring rule 1 and 2.

Safety censoring rule 1 excludes the event if it's after the permanent study drug discontinuation, or dose change, whichever occurred earlier and Safety censoring rule 2 excludes the event if it's after the permanent study drug discontinuation.

Extended Safety Analysis includes patients who were continuously treated with Baricitinib 1mg, 2mg, or 4mg and Placebo from baseline and censored in case of dose change using Safety Censoring Rule 1. In addition to the above treatment groups “ALL BARI” will also be included to the summary which includes patients who received at least one dose (1 mg, 2mg, or 4mg) of BARICITINIB at any time of the treatment period.

In an overview table, the number and percentage of patients in the safety population who experienced death, an SAE, any TEAE, discontinuation from the study due to an AE, permanent

discontinuation from study drug due to an AE, TEAEs which are considered related to treatment by the investigator, or a severe TEAE will be summarized by treatment group.

The number and percentage of patients with TEAEs will be summarized by treatment group in 2 formats:

- by MedDRA PT nested within SOC with decreasing frequency in SOC, and events ordered within each SOC by decreasing frequency in the All baricitinib group
- by MedDRA PT with events ordered by decreasing frequency in the All baricitinib group.

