#### **6.13.4.7. Major Adverse Cardiovascular Events and Other Cardiovascular Events**

Potential major adverse cardiovascular events (MACE) and other cardiovascular events requiring adjudication will be analyzed.

Categories and subcategories analyzed will include, but are not limited to the following:

- MACE
  - Cardiovascular death
  - Myocardial infarction (MI)
  - Stroke
- Other cardiovascular events
  - Transient ischemic attack
  - Hospitalization for unstable angina
  - Hospitalization for heart failure
  - Serious arrhythmia
  - Resuscitated sudden death
  - Cardiogenic shock
  - Coronary interventions (such as coronary artery bypass surgery or percutaneous coronary intervention)
- Non-cardiovascular death
- All-cause death

In general, events requiring adjudication are documented by investigative sites using an endpoint reporting CRF. This CRF is then sent to the adjudication center which uses an adjudication reporting CRF to document the final assessment of the event as a MACE, as some other cardiovascular event, or as no event (according to the Clinical Endpoint Committee Charter). In some cases, however, the investigator may not have deemed that an event had met the endpoint criteria, but the event was still sent for adjudication as a potential MACE, other cardiovascular event, or no event. These events are included in the adjudication process to ensure adequate sensitivity. In these instances, the adjudication reporting CRF will not have a matching endpoint reporting CRF from the investigator. Events generated from these circumstances will be considered as events sent for adjudication in the absence of an investigator's endpoint reporting form.

The number and percentage of patients with MACE, other cardiovascular events, non-cardiovascular death, and all-cause death, as positively adjudicated, will be summarized by treatment group based on the categories and subcategories above.

A listing of the events sent for adjudication will be provided to include data concerning the MedDRA PT related to the event, the seriousness of the event, and the event outcome, along with the adjudicated result.

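### Final-lock safety columns stop at dose change, which depends on arm by design, yet most AE tables are crude percentages, so at equal true event rates 4-mg will usually look worse than placebo

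*SAP*

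**What the plan says.** **Columns.** For the final lock, the safety row of SAP Table JAIN.6.3 groups patients by Week 0 arm, ending with "Placebo who continuously got treated from baseline and censored in case of dose change". SAP 6.13.1 describes the Extended Safety Analysis in the same way, as patients "who were continuously treated with Baricitinib 1mg, 2mg, or 4mg and Placebo from baseline and censored in case of dose change". The final-analysis safety period in SAP 6.2.1 also stops at dose change.

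**Who changes dose.** Under Protocol 5.1.3.2, patients with IGA 3 or more at Week 52 on placebo, 1-mg or 2-mg "will be automatically rerandomized at a 1:1 ratio to baricitinib 2-mg QD or baricitinib 4-mg QD". Patients with IGA 0 to 2 who are outside the substudy go through the same one-time rerandomization if they later reach IGA 3 (Protocol 5.1.3.2 and 5.1.4). Patients on 4-mg stay on 4-mg in both cases. The only planned change away from 4-mg is the substudy (Protocol 5.1.3.1), where eligible patients with IGA 0 to 2 are split 1:1 between 4-mg and 2-mg. Eligible 2-mg patients are split 1:1 between 2-mg and 1-mg.

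**Display.** The general rule in SAP 6.13.1 is that "summaries will include the number of patients in the safety population (N), frequency of patients experiencing the event (n), and relative frequency". The overview table (deaths, SAEs, TEAEs, discontinuations), the TEAE tables and the SAE tables are counts and percentages. For cardiovascular events and deaths, SAP 6.13.4.7 says: "The number and percentage of patients with MACE, other cardiovascular events, non-cardiovascular death, and all-cause death, as positively adjudicated, will be summarized". VTE (6.13.4.8) is handled likewise. Incidence rates per 100 patient-years of observation are planned at the final lock for selected safety topics (6.13.1). The only topics named are the infections of special interest in 6.13.4.6.

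**Exposure.** Duration in SAP 6.13 runs to the "date of last dose of study drug including rescue", with no stop at dose change. A second formula starts the clock after the switch for the switched groups.

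**The concern.** A crude percentage compares arms fairly only if the arms are observed for similar lengths of time. Here the observation window is closed by an event, dose change, that the design imposes on placebo and 1-mg nonresponders and never on 4-mg nonresponders. After Week 52 the placebo and 1-mg columns therefore lose patients faster than the 4-mg column, and fewer of their events can be counted.

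The result is an apparent dose gradient that comes from follow-up alone. It would sit in the long-term by-dose tables for SAEs, deaths, MACE and VTE, where a reader looks for a dose relation. The unreconciled exposure formula adds a second uncertainty: if it served as a rate denominator, events would be cut at the switch and person-time would not.

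**Working it through.** The plan gives no figure for Week 52 nonresponse, dropout, event rates or follow-up by arm, so there is nothing of its own to reproduce on this point. Everything numerical below is an assumption except the switching rules, the Week 52 switch and the Week 104 and Week 200 end points.

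**Share cut at Week 52.** Let q0 and q4 be the proportions with IGA 3 or more at Week 52 on placebo and 4-mg, and e the share of 4-mg patients with IGA 0 to 2 who are eligible for the substudy.

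- Placebo (or 1-mg): f0 = q0
- 4-mg: f4 = (1 − q4) × e × 0.5
- 2-mg: about 0.5, because both nonresponders and eligible patients with IGA 0 to 2 are split 1:1 between staying on 2-mg and leaving it

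Base case q0 = 70%, q4 = 60%, e = 90%: f0 = 0.70 and f4 = 0.40 × 0.90 × 0.5 = 0.18.

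**Crude percentage.** Take the same event rate λ = 0.05 per year in every arm, a dropout hazard d = 0.2 per year, 52 weeks = 1 year, and no later relapse switching. With h = λ + d = 0.25 and T the end of follow-up in years:

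P = (λ/h)(1 − e^(−h)) + (1 − f) e^(−h) (λ/h)(1 − e^(−h(T−1)))

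The first term is 0.2 × 0.2212 = 0.0442.

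- Week 200 (T − 1 = 148/52 = 2.846): the second term is (1 − f) × 0.7788 × 0.2 × 0.5091 = (1 − f) × 0.0793.
  - Placebo: 0.0442 + 0.30 × 0.0793 = 6.8%
  - 2-mg: 0.0442 + 0.50 × 0.0793 = 8.4%
  - 4-mg: 0.0442 + 0.82 × 0.0793 = 10.9%
  - 4-mg to placebo ratio: 1.61
- Week 104 (T − 1 = 1): the second term is (1 − f) × 0.0345.
  - Placebo 5.5%, 4-mg 7.2%, ratio 1.33

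Mean on-dose follow-up to Week 200 is 1.44 years on placebo and 2.36 years on 4-mg. That difference is the whole explanation.

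**Range over the assumptions** (λ = 0.05):

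| q0 / q4 / e | f0 / f4 | Week 200, placebo vs 4-mg (d = 0.2) | Ratio, Week 200 | Ratio, Week 104 | Ratio, Week 200, no dropout |
|---|---|---|---|---|---|
| 40 / 30 / 100% | 0.40 / 0.35 | 9.2% vs 9.6% | 1.04 | 1.03 | 1.05 |
| 50 / 50 / 90% | 0.50 / 0.225 | 8.4% vs 10.6% | 1.26 | 1.15 | 1.31 |
| 60 / 50 / 90% | 0.60 / 0.225 | 7.6% vs 10.6% | 1.39 | 1.22 | 1.48 |
| 70 / 60 / 90% | 0.70 / 0.18 | 6.8% vs 10.9% | 1.61 | 1.33 | 1.76 |
| 80 / 70 / 90% | 0.80 / 0.135 | 6.0% vs 11.3% | 1.88 | 1.45 | 2.13 |
| 85 / 50 / 100% | 0.85 / 0.25 | 5.6% vs 10.4% | 1.85 | 1.42 | 2.12 |

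Adding relapse switches among placebo responders at 0.3 per year raises the base-case Week 200 ratio to 1.79 (6.1% vs 10.9%).

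**Break-even.** With q0 = q4 = q, full eligibility and no relapse switching, placebo loses more patients than 4-mg when q > (1 − q)/2, that is, when q > 1/3. Below that the direction reverses.

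**Effect of the fix.** With events and person-time both cut at dose change, the rate is 5.0 per 100 patient-years in every arm. If person-time instead ran on to last dose (mean 2.68 years in both arms), the base case at Week 200 would read 5 × 1.44/2.68 = 2.7 on placebo and 5 × 2.36/2.68 = 4.4 on 4-mg.

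**The case against.** Five points can be made for the plan.

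- **Rates are already planned.** Incidence rates are promised at Week 52, Week 104 and final for selected topics, and the full topic list may sit in the compound-level safety standards, which are not available here. A reader might infer that AEs are shown only as crude percentages; the SAP does not support that. What stands is that the general tables and the MACE and VTE sections specify counts and percentages, and that only certain infections are named for rates.
- **A second version exists.** SAP 6.13.1 says "Adverse Events and Treatment Emergent AEs will be replicated based on the Safety Censoring rule 1 and 2", and rule 2 does not cut at dose change. It is no remedy, because it puts events that occur on baricitinib after the switch into the placebo column.
- **A comparison with equal planned follow-up exists.** There is no switch to baricitinib in Period 2, and the 52-week lock reports safety by randomized arm. This is correct and useful, but it does not repair the tables that run to Week 200.
- **Periods 3 and 4 are descriptive, without tests.** Also correct, but printed percentages are compared whether or not a p-value is attached.
- **The exposure formula may not matter.** A reader might infer that the planned rates are wrong because exposure runs past the switch. The documents do not show this. The rates use patient-years of observation, defined in the outside standard, whereas the formula in 6.13 feeds patient-years of exposure. The safety period in 6.2.1 stops at dose change, and a separate post-switch formula is given. What stands is an inconsistency between 6.13 on one side and 6.2.1, Table JAIN.6.3 and 6.13.1 on the other.

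**Conclusion.** The point holds, as a should-fix. Followed literally, the final-lock tables compare crude percentages over follow-up that differs by arm by design, and at identical true rates the 4-mg percentage will usually exceed placebo. Under the stated assumptions, with dropout of 0.2 per year and no later relapse switching, the Week 200 ratio is about 1.0 to 1.9, with a base case of 1.6. The base case at Week 104 is about 1.3. The no-dropout figures (up to 2.1 in these scenarios) are an upper bound for the same nonresponse rates, not an expectation; the SAP revision history itself describes patients being rolled off as sites close.

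It is tempting to say that most placebo and 1-mg patients switch at Week 52 and few 4-mg patients do. The documents give no nonresponse rates, and half of the eligible 4-mg patients with IGA 0 to 2 are down-titrated, so only the direction is likely, and its size is open. No hypothesis test, efficacy claim or Week 0–52 safety comparison depends on this display.

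**What to change.** In SAP 6.13 and 6.13.1, for the final lock and for any 104-week table using the same dose-change-censored columns:

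1. Add the incidence rate per 100 patient-years at risk, with 95% CI, to the overview, TEAE, SAE, AE-discontinuation and AESI tables. State that dose columns are compared on this rate and not on n/N.
2. End person-time at risk on the same date as event counting in each column.
3. Reconcile the exposure formula in 6.13 with 6.2.1, Table JAIN.6.3 and the Extended Safety Analysis text, by computing by-dose exposure to the last dose before dose change.
4. Refer crude between-arm percentages to the Week 0–52 window.

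Rates remove the artefact of unequal follow-up but not the selection: after Week 52 the placebo and 1-mg columns hold only patients with IGA below 3. That is a further reason for item 4. The cost is SAP wording and extra table columns; no new data are needed.

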The time period for safety analysis of the 24-week interim analysis will be following criteria whichever occurs first:

- up to last dose plus up to 30 days in the study
- the first dose in Period 3
- up to dose change or up to the data cutoff date

The time period for safety analysis of the 52-week interim analysis will be following criteria whichever occurs first:

- up to last dose plus up to 30 days in the study
- the study discontinuation date
- up to dose change
- the first dose date in Period 3

**The time period for safety analysis of the 104 interim analysis** will be following criteria whichever occurs first:

- up to last dose plus up to 30 days in the study
- the study discontinuation date
- up to dose change date due to rescue

- up to dose change date due to retreatment
- the first dose in Period 4
- up to the data cutoff date

**The time period for safety analysis of the final analysis** will be following criteria whichever occurs first:

- up to last dose plus 30 days or up to last date in the study
- the study discontinuation date
- up to dose change

**Long-Term Extension (LTE) Substudy Population:** The LTE Substudy Population is defined as the patients who received at least one study medication in Period 3 of Study JAIN, and entered the downtitration substudy. Additionally, those patients who did not met study discontinuation criteria in Period 3 and continued in Period 4 will be considered in the analysis set.

**Long-Term Extension(LTE) Substudy Relapse Population:** for a subset of patients in the LTE Substudy Population defined as above who experienced a relapse in Period 3 or Period 4 (IGA $\geq$ 3 after Week 52).

**Long-Term Extension(LTE) Non-responder Population:** The LTE Non-responder Population is defined as the patients who received at least one study medication in Period 3 of Study JAIN, and IGA $\geq$ 3 at Week 52. Additionally, those patients who did not met study discontinuation criteria in Period 3 and continued in Period 4 will be considered in the analysis set.

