## 6.13. Safety Analyses

The general methods used to summarize safety data, including the definition of baseline value are described in Section 6.2.2.

Safety analyses will include all data including rescue to any of the 3 rescue therapy options, unless otherwise stated, and patients will be analyzed according to the investigational product to which they were randomized at Week 0 (Visit 2). For 24-week and 52-week interim lock, safety analyses will use the safety population defined in Section 6.2.1.

For the 24-week and 52-week interim lock, safety topics that will be addressed include the following: AEs, clinical laboratory evaluations, vital signs and physical characteristics, Columbia Suicide Severity Rating Scale (C-SSRS), the Self-Harm Supplement Form, safety in special groups and circumstances, including adverse events of special interest (AESI) (see Section 6.13.4), and investigational product interruptions.

Unless otherwise specified, by-visit summaries will include planned on-treatment visits. For tables that summarize events (such as AEs, categorical laboratory abnormalities, shift to maximum severity), post-last dose follow-up data will be included. Follow-up data is defined as all data occurring up to 30 days (planned maximum follow-up time) after last dose of treatment including rescue, regardless of study period. All safety data from continuing patients at time of the 52-week interim lock will be included in the safety analysis up to the first dose date of period 3. Safety data from patients who permanently discontinued study drug prior to an interim lock will be included in the interim lock safety analysis up to 30 days post last dose.

For the 104-week interim analysis safety topics will be addressed including the following: AEs and AESI (i.e., infections, MACE, VTE, Malignancies).

For the final analyses, safety analyses will use the safety population and Extended Safety analysis will be performed by treatment based on the initial randomization at week 0 including the All BARI group, who received at least one dose of BARI during the study, to address both the safety topics including AEs and AESI (i.e., infections, MACE, VTE, Malignancies). The Compound level safety standards provide further details and information.

Duration of exposure (in days) will be calculated as follows:

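### Both safety censoring rules in SAP 6.13.1 stop counting adverse events at permanent drug discontinuation, while the SAP's own safety windows run to 30 days after last dose

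*SAP*

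**What the plan says.** SAP 6.13.1 (Adverse Events) gives two rules. For the first: "Safety censoring rule 1 excludes the event if it's after the permanent study drug discontinuation, or dose change, whichever occurred earlier". For the second: "Safety censoring rule 2 excludes the event if it's after the permanent study drug discontinuation". It then says "Adverse Events and Treatment Emergent AEs will be replicated based on the Safety Censoring rule 1 and 2". The Extended Safety Analysis, which follows patients treated continuously from baseline, is "censored in case of dose change using Safety Censoring Rule 1". SAP 6.13 makes that the final safety analysis, covering adverse events and events of special interest (infections, MACE, VTE, malignancies). The Revision History (SAP Section 3) records that the censoring-rule text was added in Version 5 for the final lock.

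Other parts of the SAP set a longer window. For treatment-emergent events, 6.13.1 itself says "The analysis period is defined as the treatment period plus up to 30 days off-drug follow-up time". SAP 6.13 puts post-last-dose data into event tables: "Follow-up data is defined as all data occurring up to 30 days (planned maximum follow-up time) after last dose of treatment including rescue". For the final analysis, 6.2.1 takes the earliest of three limits. The first is "up to last dose plus 30 days or up to last date in the study"; the other two are study discontinuation and dose change. Stopping drug is not a cut-off there. For patients who stopped drug before an interim lock, 6.13 says their data "will be included in the interim lock safety analysis up to 30 days post last dose". Protocol 5.1.5 schedules the follow-up visit (Visit 801) about 28 days after last dose.

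**The concern.** A programmer cannot apply the 30-day treatment-emergent window and a censoring rule that ends at drug discontinuation in the same table. If the rules are followed as written, events that begin in the weeks after stopping leave the final adverse-event and special-interest tables in every arm. The sites have been asked to collect exactly those weeks at Visit 801. The loss falls only on patients who stop drug, and it would make the final tables disagree with the 52-week tables for the same patients.

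Two lesser gaps sit beside this. The second rule does not cut at dose change, and no section names the columns it is reported in. All BARI admits anyone who ever took baricitinib, but the SAP does not say which part of a placebo switcher's follow-up counts.

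**Working it through.** The core of the check is textual.

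| Source in SAP | End of counting after drug is stopped |
|---|---|
| 6.2.1, final analysis | Last dose plus 30 days or last date in study, unless study discontinuation or dose change comes first |
| 6.13, event tables | Up to 30 days after last dose |
| 6.13.1, treatment-emergent definition | Up to 30 days off drug, and no later than the last visit in the period |
| 6.13.1, rule 1 | Permanent drug discontinuation (or earlier dose change) |
| 6.13.1, rule 2 | Permanent drug discontinuation |

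Take a patient who stops drug at Week 24 and, while still in the study, has a new non-serious event 10 days later. At the 52-week lock, 6.2.1 and 6.13 count it. At the final lock, 6.2.1 and the treatment-emergent definition count it, but both rules exclude it. The dose-change cut in rule 1 agrees with 6.2.1; only the discontinuation cut conflicts.

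**Size.** The documents give no discontinuation rates, so the figures below rest on assumptions. They use the full 30 days, and the window is only up to 30 days, so they are upper bounds on its length.

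Share of one patient's safety observation that lies in the window, stopping at week w: 30/(7w + 30).

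- w = 4: 30/58 = 51.7%
- w = 12: 30/114 = 26.3%
- w = 24: 30/198 = 15.2%
- w = 52: 30/394 = 7.6%

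Share of an arm's observation, if a fraction d stops at Week 24 and the rest are followed to week T: 30d/[198d + 7T(1 − d)].

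| T | d = 0.1 | d = 0.4 |
|---|---|---|
| 52 | 3/(19.8 + 327.6) = 0.86% | 12/(79.2 + 218.4) = 4.03% |
| 104 | 3/(19.8 + 655.2) = 0.44% | 12/(79.2 + 436.8) = 2.33% |
| 200 | 3/(19.8 + 1260) = 0.23% | 12/(79.2 + 840) = 1.31% |

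T = 52 is relevant because rule 1 cuts patients whose dose changes at Week 52. Earlier stopping raises the share: with d = 0.4, T = 52 and stopping at Week 4 it is 12/(0.4 × 58 + 0.6 × 364) = 12/241.6 = 5.0%.

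**Secondary gaps, by text only.** Section 6.2.1 (final) and the Safety Population row of Table JAIN.6.3, which lists All Bari, cut at dose change. Section 6.2.2.1 sets the final-lock adverse-event baseline at Week 0. Section 6.13.1 admits to All BARI any patient with at least one baricitinib dose at any time. Applied together and literally, a placebo patient rerandomized to baricitinib at Week 52 would enter All BARI because of the baricitinib dose, yet contribute only placebo time. For rule 2, if patients are grouped by Week 0 randomization, as 6.13 does generally, that patient's baricitinib-period events would appear under placebo.

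**The case against.** The strongest reply is that the replication sentence describes extra runs beside the standard 30-day tables, so nothing is lost. That is a fair reading of the sentence. It does not settle the matter, because the Extended Safety Analysis is tied to rule 1 by name and is the final safety analysis. The intention may have been only to cut at dose change, but the rule as defined also cuts at drug discontinuation.

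A second reply is that the damage is contained, and this largely stands. All SAEs are listed, and deaths are listed whenever they occurred (6.13.1.2). Malignancies are kept whatever the gap since last dose (6.13.4.10). Under 6.2.1, 6.13 and the treatment-emergent definition, the 24- and 52-week tables keep up to 30 days. A reader might infer that events which caused patients to stop are lost. They are not: their onset precedes discontinuation, and 6.13.1.3 summarizes them separately. Only later-onset events are at issue.

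A reader might also infer a mismatch with the laboratory analyses, because 6.13.2 keeps 30 days for categorical results. The documents do not show one. Section 6.13 plans laboratory evaluations for the 24- and 52-week locks only, and the censoring rules were added for the final lock.

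Finally, 6.13 and 6.13.1 refer to the Compound level safety standards, which are not available here. They may resolve the secondary gaps. They cannot make conflicting sentences within the SAP agree.

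**Conclusion.** The conflict is real and is visible in the text without any assumed rate. Both rules omit the off-drug window that 6.2.1, 6.13 and the treatment-emergent definition provide, and rule 1 governs the final safety analysis. The consequence is modest: roughly 0.2–4% of arm observation time if 10–40% stop at Week 24, and somewhat more if they stop earlier. The per-patient shares are larger, but they apply only to patients who stop and assume the full 30 days. SAP 6.2.2.3 makes Period 3 and 4 safety descriptive, so no formal test in those periods depends on this. It should still be corrected, because the final and 52-week tables could otherwise differ for the same patients for no clinical reason.

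The rule 2 and All BARI points are ambiguities, not demonstrated errors. A reader might conclude that much of the placebo column, or of All BARI, will be misattributed. The documents do not support a figure for either: no section assigns columns to rule 2, rule 2 may have been meant for All BARI, and the Compound level safety standards could not be checked. Nor do the post-switch exposure formulas in 6.13 settle All BARI, since they also restart exposure at changes from one baricitinib dose to another.

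**What to change.** Reword both rules in SAP 6.13.1 to exclude events after permanent study drug discontinuation plus up to 30 days, in line with 6.2.1, 6.13 and the treatment-emergent definition. Keep the dose-change cut in rule 1 and the malignancy exception in 6.13.4.10. State whether the rule 1 and rule 2 runs replace or supplement the standard treatment-emergent tables.

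Name the columns reported under rule 2, so that events of rerandomized placebo patients after the switch are not shown under placebo. Reconcile 6.2.1, Table JAIN.6.3, 6.2.2.1 and 6.13.1 so that a placebo-to-baricitinib switcher contributes baricitinib time, and not placebo time, to All BARI, subject to the Compound level safety standards.

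The cost is SAP wording and reprogramming of safety data already collected. If rule 2 had been planned by Week 0 arm, placebo follow-up in those tables becomes shorter.
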